8.2.5. Pregnancy Testing

Pregnancy tests may be urine or serum tests, but must have a sensitivity of at least 25 mIU/mL. Pregnancy tests will be performed in WOCBP at the times listed in the [Schedule of Activities](#). WOCBP must be using a permitted contraceptive method to be eligible for study participation (see [Appendix 4 Section 10.4.4](#)). A negative pregnancy test result at screening and a second negative pregnancy test result at the baseline visit are required prior the participant's receiving the investigational product. Pregnancy tests will also be done whenever 1 menstrual cycle is missed during the active treatment period (or when potential pregnancy is otherwise suspected) and at the end of the study. Pregnancy tests may also be repeated if requested by institutional review boards (IRBs)/ethics committees (ECs) or if required by local regulations.

8.3. Adverse Events and Serious Adverse Events

The definitions of an AE and an SAE can be found in [Appendix 3](#).

AEs will be reported by the participant (or, when appropriate, by a caregiver, surrogate, or the participant's legally authorized representative).

The investigator and any qualified designees are responsible for detecting, documenting, and recording events that meet the definition of an AE or SAE and remain responsible to pursue and obtain adequate information both to determine the outcome and to assess whether it meets the criteria for classification as an SAE or that caused the participant to discontinue the study (see [Section 7](#)).

In addition, the investigator may be requested by Pfizer Safety to obtain specific follow-up information in an expedited fashion.

8.3.1. Time Period and Frequency for Collecting AE and SAE Information

The time period for actively eliciting and collecting AEs and SAEs ("active collection period") for each participant begins from the time the participant provides informed consent, which is obtained before the participant's participation in the study (ie, before undergoing any study-related procedure and/or receiving investigational product), through and including a minimum of 28 calendar days after the last administration of the investigational product(s).

For participants who are screen failures, the active collection period ends when screen failure status is determined.

Medical occurrences that begin before the start of study intervention but after obtaining informed consent will be recorded on the Medical History/Current Medical Conditions section of the CRF, not the AE section.

Follow-up by the investigator continues throughout and after the active collection period and until the event or its sequelae resolve or stabilize at a level acceptable to the investigator, and Pfizer concurs with that assessment.

Investigators are not obligated to actively seek AE or SAE after conclusion of the study participation. However, if the investigator learns of any SAE, including a death, at any time after a participant has been discharged from the study, and he/she considers the event to be reasonably related to the study intervention or study participation, the investigator must promptly notify the sponsor.

8.3.1.1. Reporting SAEs to Pfizer Safety

All SAEs occurring in a participant during the active collection period are reported to Pfizer Safety on the CT SAE Report Form immediately and under no circumstance should this exceed 24 hours, as indicated in [Appendix 3](#). The investigator will submit any updated SAE data to the sponsor within 24 hours of it being available.

SAEs occurring in a participant after the active collection period has ended are reported to Pfizer Safety if the investigator becomes aware of them; at a minimum, all SAEs that the investigator believes have at least a reasonable possibility of being related to investigational product must be reported to Pfizer Safety.

8.3.1.2. Recording Nonserious AEs and SAEs on the CRF

During the active collection period, both nonserious AEs and SAEs are recorded on the CRF.

8.3.2. Method of Detecting AEs and SAEs

The method of recording, evaluating, and assessing causality of AEs and SAEs and the procedures for completing and transmitting SAE reports are provided in [Appendix 3](#).

Care will be taken not to introduce bias when detecting AEs and/or SAEs. Open-ended and nonleading verbal questioning of the participant is the preferred method to inquire about AE occurrences.

8.3.3. Follow-up of AEs and SAEs

After the initial AE/SAE report, the investigator is required to proactively follow each participant at subsequent visits/contacts. For each event, the investigator must pursue and obtain adequate information until resolution, stabilization, the event is otherwise explained, or the participant is lost to follow-up (as defined in [Section 7.3](#)).

In general, follow-up information will include a description of the event in sufficient detail to allow for a complete medical assessment of the case and independent determination of possible causality. Any information relevant to the event, such as concomitant medications and illnesses, must be provided. In the case of a participant death, a summary of available autopsy findings must be submitted as soon as possible to Pfizer Safety.

Further information on follow-up procedures is given in [Appendix 3](#).

8.3.4. Regulatory Reporting Requirements for SAEs

Prompt notification by the investigator to the sponsor of an SAE is essential so that legal obligations and ethical responsibilities towards the safety of participants and the safety of a study intervention under clinical investigation are met.

The sponsor has a legal responsibility to notify both the local regulatory authority and other regulatory agencies about the safety of a study intervention under clinical investigation. The sponsor will comply with country-specific regulatory requirements relating to safety reporting to the regulatory authority, institutional review boards (IRBs)/ECs, and investigators.

Investigator safety reports must be prepared for suspected unexpected serious adverse reactions (SUSARs) according to local regulatory requirements and sponsor policy and forwarded to investigators as necessary.

An investigator who receives an investigator safety report describing an SAE or other specific safety information (eg, summary or listing of SAEs) from the sponsor will review and then file it along with the investigator's brochure and will notify the IRB/EC, if appropriate according to local requirements.

8.3.5. Exposure During Pregnancy or Breastfeeding, and Occupational Exposure

Exposure to the investigational product under study during pregnancy or breastfeeding and occupational exposure are reportable to Pfizer Safety within 24 hours of investigator awareness.

8.3.5.1. Exposure During Pregnancy

Details of all pregnancies in female participants and, if indicated, female partners of male participants will be collected after the start of study intervention and until 28 days after the last dose.

If a pregnancy is reported, the investigator should inform the sponsor within 24 hours of learning of the pregnancy and should follow the procedures outlined in [Appendix 4](#).

Abnormal pregnancy outcomes (eg, spontaneous abortion, fetal death, stillbirth, congenital anomalies, ectopic pregnancy) are considered SAEs.

8.3.5.2. Exposure During Breastfeeding

Scenarios of exposure during breastfeeding must be reported, irrespective of the presence of an associated SAE, to Pfizer Safety within 24 hours of the investigator's awareness, using the CT SAE Report Form. An exposure during breastfeeding report is not created when a Pfizer drug specifically approved for use in breastfeeding women (eg, vitamins) is administered in accord with authorized use. However, if the infant experiences an SAE associated with such a drug's administration, the SAE is reported together with the exposure during breastfeeding.

8.3.5.3. Occupational Exposure

An occupational exposure occurs when, during the performance of job duties, a person (whether a healthcare professional or otherwise) gets in unplanned direct contact with the product, which may or may not lead to the occurrence of an AE.

An occupational exposure is reported to Pfizer Safety within 24 hours of the investigator's awareness, using the CT SAE Report Form, regardless of whether there is an associated SAE. Since the information does not pertain to a participant enrolled in the study, the information is not recorded on a CRF; however, a copy of the completed CT SAE Report Form is maintained in the investigator site file.

8.3.6. Medication Errors

Medication errors may result from the administration or consumption of the investigational products by the wrong participant, or at the wrong time, or at the wrong dosage strength.

Exposures to the investigational product under study may occur in clinical trial settings, such as medication errors.

Safety Event	Recorded on the CRF	Reported on the CT SAE Report Form to Pfizer Safety Within 24 Hours of Awareness
Medication errors	All (regardless of whether associated with an AE)	Only if associated with an SAE

Medication errors include:

- Medication errors involving participant exposure to the investigational products;
- Potential medication errors or uses outside of what is foreseen in the protocol that do or do not involve the study participant.

Such medication errors occurring to a study participant are to be captured on the medication error page of the CRF, which is a specific version of the AE page.

In the event of a medication dosing error, the sponsor should be notified immediately.

Whether or not the medication error is accompanied by an AE, as determined by the investigator, the medication error is recorded on the medication error page of the CRF and, if applicable, any associated AE(s), serious and nonserious, are recorded on an AE page of the CRF.

Medication errors should be reported to Pfizer Safety within 24 hours on a CT SAE Report Form only when associated with an SAE.

8.4. Treatment of Overdose

For this study, any dose of PF-06651600 greater than 800 mg within a 24-hour time period will be considered an overdose.

There is no specific antidote or specific treatment for an overdose of PF-06651600.

In the event of an overdose, the investigator should:

1. Contact the medical monitor immediately.
2. Closely monitor the participant for any AEs/SAEs and laboratory abnormalities until PF-06651600 can no longer be detected systemically (at least 4 days).
3. Obtain a blood sample for PK analysis within 4 days from the date of the last dose of study intervention if requested by the medical monitor (determined on a case-by-case basis).
4. Document the quantity of the excess dose as well as the duration of the overdose in the CRF.
5. Overdose is reportable to Safety only when associated with an SAE.

Decisions regarding dose interruptions or modifications will be made by the investigator in consultation with the medical monitor based on the clinical evaluation of the participant.

8.5. Pharmacokinetics

8.5.1. Plasma for Analysis of PF-06651600

Blood samples of approximately 3 mL, to provide approximately 1 mL plasma, will be collected for measurement of plasma concentrations of PF-06651600 as specified in the [Schedule of Activities](#). Instructions for the collection and handling of biological samples will be provided in the laboratory manual or by the sponsor. The actual date and time (24-hour clock time) of each sample will be recorded.

The actual times may change, but the number of samples will remain the same. All efforts will be made to obtain the samples at the exact nominal time relative to dosing. Collection of samples up to and including 10 hours after dose administration that are obtained within 10% of the nominal time (eg, within 6 minutes of a 60-minute sample) relative to dosing will not be captured as a protocol deviation, as long as the exact time of the collection is noted on

the source document and data collection tool (eg, CRF/DCT). Collection of samples more than 10 hours after dose administration that are obtained ≤ 1 hour away from the nominal time relative to dosing will not be captured as a protocol deviation, as long as the exact time of the collection is noted on the source document and data collection tool (eg, CRF/DCT).

Samples will be used to evaluate the PK of PF-06651600. Samples collected for analyses of PF-06651600 concentration may also be used to evaluate safety or efficacy aspects related to concerns arising during or after the study, for metabolite identification and/or evaluation of the bioanalytical method, or for other internal exploratory purposes.

Genetic analyses will not be performed on these plasma. Participant confidentiality will be maintained.

Samples collected for measurement of plasma concentrations of PF-06651600 will be analyzed using a validated analytical method in compliance with applicable standard operating procedures (SOPs).

The PK samples must be processed and shipped as indicated in the instructions provided to the investigator site to maintain sample integrity. Any deviations from the PK sample handling procedure (eg, sample collection and processing steps, interim storage or shipping conditions), including any actions taken, must be documented and reported to the sponsor. On a case-by-case basis, the sponsor may make a determination as to whether sample integrity has been compromised.

8.5.2. Urine for Analysis of PF-06651600

Urine will be collected at the intervals outlined in [Schedule of Activities](#). Each participant will empty his/her bladder just prior to dosing. During the subsequent designated urine collection intervals ([0-6], [6-12], and [12-24] hours post dose), participants will void ALL urine produced during the designated collection interval, including a forced void at the end of the collection interval, directly into pre-weighed urine collection container. Each collection interval should have its own collection container(s). During the entire collection interval, the container(s) should be stored at 4°C. At the end of each urine collection interval, all urine collected will be thoroughly mixed, the total volume will be measured and recorded on the CRF. An urine aliquot will be withdrawn for measurement of drug concentrations.

Additional details for collection, processing and storage of urine for analysis of PF-06651600 will be added to the laboratory manual and provided to the investigator site prior to the start of the study.

Urine samples will be analyzed using a validated analytical method in compliance with Pfizer SOPs, **only** if it is determined by the study team that there is a need to do so, based on review of plasma PK results for PF-06651600.

8.6. Pharmacodynamics

PD parameters are not evaluated in this study.

8.7. Genetics

8.7.1. Specified Genetics

Genetics (specified analyses) are not evaluated in this study.

8.7.2. Banked Biospecimens for Genetics

A 4-mL blood sample optimized for deoxyribonucleic acid (DNA) isolation (Prep D1) will be collected as local regulations and IRBs/ECs allow.

Banked biospecimens may be used for research related to drug response. Genes and other analytes (eg, proteins, RNA, nondrug metabolites) may be studied using the banked samples.

Unless prohibited by local regulations or IRB/EC decision, participants will be asked to indicate on the consent document whether they will allow their banked biospecimens to also be used to design and conduct research in order to gain a further understanding of other diseases and to advance science, including development of other medicines for patients. This component of the sampling banking is optional for participants; they may still participate in the study even if they do not agree to the additional research on their banked biospecimens. The optional additional research does not require the collection of any further samples.

See [Appendix 5](#) for information regarding genetic research. Details on processes for collection and shipment of these samples can be found in lab manual and other supporting documentation.

8.8. Biomarkers

Biomarkers are not evaluated in this study.

8.8.1. Specified Gene Expression (RNA) Research

Specified gene expression (RNA) research is not included in this study.

8.8.2. Specified Protein Research

Specified protein research is not included in this study.

8.8.3. Specified Metabolomic Research

Specified metabolomic research is not included in this study.

8.9. Health Economics

Health economics/medical resource utilization and health economics parameters are not evaluated in this study.

9. STATISTICAL CONSIDERATIONS

Detailed methodology for summary and statistical analyses of the data collected in this study is outlined here and further detailed in a statistical analysis plan (SAP), which will be maintained by the sponsor. The SAP may modify what is outlined in the protocol where appropriate; however, any major modifications of the primary endpoint definitions or their analyses will also be reflected in a protocol amendment.

9.1. Statistical Hypotheses

No statistical hypothesis will be tested in this study.

9.2. Sample Size Determination

In Part 1, approximately 8 participants will be enrolled into the normal renal function group and the severe renal impairment group to ensure approximately 6 evaluable completers in each group. If Part 2 is conducted, approximately 8 participants will be enrolled to the mild and moderate renal groups to ensure approximately 6 evaluable completers per group. The sample size is based on recommendations from the “FDA Guidance for Industry - Pharmacokinetics in Patients with Impaired Renal Function-Study Design, Data Analysis, and Impact on Dosing and Labeling”.⁵

Participants who discontinue from the study before completing all assessments may be replaced at the discretion of the investigator and Sponsor.

9.3. Populations for Analysis

For purposes of analysis, the following populations are defined:

Population	Description
PK Concentration	The PK concentration population is defined as all participants assigned to investigational product and treated who have at least 1 concentration measured.
PK Parameter	The PK parameter analysis population is defined as all participants assigned to investigational product and treated who have at least 1 of the PK parameters of primary interest measured.
Safety	All assigned to investigational product and who take at least 1 dose of investigational product. Participants will be analyzed according to the product they actually received.

9.4. Statistical Analyses

The SAP will be developed and finalized before database lock and will describe the participant populations to be included in the analyses, and procedures for accounting for missing, unused, and spurious data. This section is a summary of the planned statistical analyses of the primary and secondary endpoints.

Part 1

Analysis of variance (ANOVA) will be used to compare the natural log transformed PF-06651600 AUC_{0-24} and C_{max} between normal renal function group (Reference) and the severe impaired renal function group (Test). Estimates of the adjusted mean differences (Test-Reference) and corresponding 90% confidence intervals (CIs) will be obtained from the model. The mean differences and 90% CIs for the differences will be exponentiated to provide estimates of the ratio of the geometric means (Test/Reference) and 90% CIs for the ratios.

Part 2 may be conducted if PF-06651600 AUC_{0-24} GMR for severe renal impairment group compared to normal group is ≥ 2 .

Part 2

ANOVA will be used to compare the natural log transformed PF-06651600 AUC_{0-24} and C_{max} between normal renal function group (Reference) and the moderate and mild impaired renal function groups (Test). Estimates of the adjusted mean differences (Test-Reference) and corresponding 90% CIs will be obtained from the model. The mean differences and 90% CIs for the differences will be exponentiated to provide estimates of the ratio of the geometric means (Test/Reference) and 90% CIs for the ratios. If substantial differences in demographic characteristics between healthy and impaired participants are observed, weight and age will be explored as covariates.

Box and whisker plots for individual participant parameters (AUC_{0-24} and C_{max}) will be constructed by renal function group and overlaid with geometric means.

For summary statistics and median/mean plots by sampling time, the nominal PK sampling time will be used. For individual participant plots by time, the actual PK sampling time will be used.

If Part 2 is executed and data for normal, mild, moderate and severe impairment groups are available, additional analysis will be performed to assess relationship between appropriate PK parameters and renal function.

Linear regression will be used to analyze the potential relationship between appropriate PK parameters (CL/F or CL_r , and V_z/F) and renal function (eGFR). Estimates of the slope and, intercept, together with their precision (90% CI), and the coefficient of determination will be obtained from the model.

Plots of PK parameters (CL/F or CL_r , and V_z/F) versus renal function (eGFR) will be constructed. A regression line and 90% confidence region for the PK parameters and eGFR will be included if appropriate. Vertical lines for the renal function group cut-off values will also be presented on the plots. Different symbols will be used to identify participants from different renal function groups.

9.4.1. Efficacy Analyses

An efficacy analysis is not applicable to this study.

9.4.2. Safety Analyses

All safety analyses will be performed on the safety population.

AEs, ECGs, BP, pulse rate, and safety laboratory data will be reviewed and summarized on an ongoing basis during the study to evaluate the safety of participants. Any clinical laboratory, ECG, BP, and pulse rate abnormalities of potential clinical concern will be described. Safety data will be presented in tabular and/or graphical format and summarized descriptively, where appropriate.

Medical history and physical examination and neurological examination information, as applicable, collected during the course of the study will be considered source data and will not be required to be reported, unless otherwise noted. However, any untoward findings identified on physical and/or neurological examinations conducted during the active collection period will be captured as AEs, if those findings meet the definition of an AE. Data collected at screening that are used for inclusion/exclusion criteria, such as laboratory data, ECGs, and vital signs, will be considered source data, and will not be required to be reported, unless otherwise noted. Demographic data collected at screening will be reported.

9.4.3. Other Analyses

Genomic banked biospecimens will be collected and retained for future analyses, but will not be analyzed, specifically, for this study.

9.4.3.1. Pharmacokinetic Analyses

9.4.3.1.1. Analysis Population

The PK concentration population will be defined as all participants treated in whom at least 1 plasma concentration value is reported.

The PK parameter analysis population is defined as all participants dosed who have at least 1 of the PK parameters of primary interest.

9.4.3.1.2. Derivation of Pharmacokinetic Parameters Prior to Analysis

The plasma PK parameters for PF-06651600 following multiple dose administration will be derived from the concentration time profiles as detailed in Table 3. Actual PK sampling times will be used in the derivation of PK parameters. In the case that actual PK sampling times are not available, nominal PK sampling time will be used in the derivation of PK parameters.

Table 3. Plasma PK Parameters

Parameter	Definition	Method of Determination
AUC ₀₋₂₄	Area under the plasma concentration-time profile from time 0 to 24 hours	Linear/Log trapezoidal method.
AUC _{last}	Area under the plasma concentration-time profile from time 0 to the time of the last quantifiable concentration (C _{last})	Linear/Log trapezoidal method.
C _{max}	Maximum plasma concentration	Observed directly from data.
T _{max}	Time for C _{max}	Observed directly from data as time of first occurrence.
CL/F	Apparent clearance	Calculated as AUC ₀₋₂₄ /Dose.
C _{trough}	Pre-dose concentration	Observed from data as pre-dose concentrations on Days 8 – 10.

If urine samples need to be analyzed (See [Section 8.5.2](#)), the following urine PK parameters (Table 4) will be calculated for PF-06651600 (as data permit):

Table 4. Urine PK Parameters		
Parameter	Definition	Method of Determination
Ae ₂₄	Total amount of unchanged drug excreted in the urine over 24 hours	Sum of amount excreted for each collection period.
Ae ₂₄ %	Total amount of unchanged drug excreted in the urine over 24 hours, expressed as percent of dose	100(Ae ₂₄ /Dose)
CL _r	Renal clearance	Ae ₂₄ /AUC ₂₄

Urine PK parameters will be analyzed and summarized using descriptive statistics.

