2.1. Study Rationale

The primary purpose of this non-randomized, multiple dose, open-label study is to characterize the effect of renal impairment on the plasma pharmacokinetics (PK) of PF-06651600 following administration of multiple 50 mg oral doses. CCI [REDACTED]

[REDACTED]. In the first in human study, B7981001, urinary recovery ($Ae_t\%$) of PF-06651600 was low, with <8% of the dose recovered unchanged in urine, indicating that the renal pathway plays a minimal role in PF-06651600 excretion.

Evidence suggests that the PK of drugs that are not only excreted by the kidney can be affected by renal impairment through inhibition of pathways of hepatic and gut drug metabolism and transport.¹ Consequently, recent European Medicines Agency (EMA) guidelines suggest that renal impairment studies be conducted in patients with decreased renal function for nearly all small molecules, even if the drug or its active metabolite is not primarily eliminated by the kidneys.² The revised Food and Drug Administration (FDA) Draft Guidance on renal impairment studies also recommends that a PK study be conducted in participants with renal impairment when the drug is likely to be used in patients with impaired renal function.¹

PF-06651600 is intended for chronic use in patients, some of whom may have some degree of impaired renal function. Therefore, the purpose of this study is to characterize the effect of renal impairment on the plasma PK of PF-06651600. Findings from this study will be used to develop dosing recommendations so that the dose and/or dosing interval may be adjusted appropriately in the presence of renal disease.

CCI [REDACTED]

CCI [REDACTED]

[REDACTED]

[REDACTED]

[REDACTED]

[REDACTED]

[REDACTED]

[REDACTED]

[REDACTED]

CCI [REDACTED]

[REDACTED]

[REDACTED]

[REDACTED]

[REDACTED]

[REDACTED]

[REDACTED]

CCI

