3. OBJECTIVES AND ENDPOINTS

Objectives	Endpoints
Primary:	Primary:

 Part 1: To evaluate the effect of severe renal impairment on the PK of PF-06651600 following multiple oral dose administration. Part 2 (if applicable): To evaluate the effect of moderate and mild renal impairment on the PK of PF-06651600 following multiple oral dose administration. 	
 Plasma PF-06651600 PK parameters: C_{max} and AUC_{0-24}.
Secondary:	Secondary:

 To evaluate the safety and tolerability of multiple oral doses of PF-06651600 in participants with renal impairment and in healthy participants with normal renal function. 	
 Safety: treatment-emergent adverse events, clinical laboratory tests, vital signs, physical exam and ECGs.
Tertiary/Exploratory:	Tertiary/Exploratory:

 To compare additional PK parameters of PF-06651600 following administration of multiple oral doses in participants with renal impairment and in healthy participants without renal impairment. To enable exploratory research through collection of banked biospecimens, unless prohibited by local regulations or ethics committee decision. 	
 Plasma PF-06651600 PK parameters: T_{max}, AUC_{last}, CL/F, and C_{trough} on Days 8, 9, 10 and 11. Potential results from exploratory analysis of banked biospecimens (these results may or may not be generated in the context of the present study).

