### **6.3. Other Endpoints**

#### **6.3.1. PK Endpoints**

Blood and urine samples for PK analysis of PF-06651600 will be taken according to the Schedule of Activities given in the protocol.

The following PK parameters will be calculated for PF-06651600 (if possible) from the concentration-time data using standard noncompartmental methods:

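### Protocol Table 3 gives CL/F as AUC0-24 divided by Dose, the reciprocal of apparent clearance; followed literally, CL/F contrasts between renal groups would point the wrong way

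*Protocol*

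**What the plan says.** Protocol section 9.4.3.1.2 states that plasma parameters are derived as set out in its Table 3. The CL/F row carries the definition of apparent clearance and the method "Calculated as AUC ₀₋₂₄ /Dose". The abbreviation list in Appendix 9 also expands CL/F as apparent clearance.

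Table 4 in the same section gives the urine parameters. Ae24% is 100(Ae24/Dose), described as "Total amount of unchanged drug excreted in the urine over 24 hours, expressed as percent of dose", and CLr is Ae24/AUC24.

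The SAP gives no formula for CL/F. Section 6.3.1 says that parameters come "from the concentration-time data using standard noncompartmental methods".

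CL/F is used in two places:

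- **Group summaries.** It is listed in protocol section 3 under the exploratory objective "To compare additional PK parameters of PF-06651600 following administration of multiple oral doses in participants with renal impairment". SAP Table 3 puts it on the natural-log scale for descriptive display, and SAP Table 4 summarises it by renal function group.
- **Part 2 regression.** Protocol section 9.4 and SAP section 8.2 name CL/F or CLr, together with Vz/F, for a regression on eGFR: "Linear regression will be used to analyze the potential relationship between appropriate PK parameters". This is done only "If Part 2 is executed and data for normal, mild, moderate and severe impairment groups are available".

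**The concern.** A clearance relates dose to exposure with exposure in the denominator: at a fixed dose, higher AUC means lower clearance. Table 3 has the fraction upside down, so the quantity it defines rises when clearance falls. The CLr formula in Table 4 has AUC in the denominator, so the two clearances in this section run in opposite directions.

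If Table 3 were programmed as written, the CL/F summaries in Part 1, and in Part 2 if it is run, would reverse every group difference in which AUC0-24 differs. A reader would see clearance increasing with renal impairment just where exposure shows that it decreases. The study is meant to support dosing recommendations in renal disease, so a clearance table pointing the wrong way could mislead, even though it is exploratory.

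**Working it through.** **Inputs from the documents.** Dose is 50 mg once daily in all groups, with no dose modification (protocol sections 4.1 and 6.6). The AUC0-24 ratio that triggers Part 2 is 2.0 (section 4.1). For urinary recovery, section 2.1 reports the first-in-human study "with <8% of the dose recovered unchanged in urine". The documents give no AUC or CL/F values, so the AUC values below are assumptions for illustration.

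**Units.** With dose in mg and AUC in mg·h/L:

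- Dose/AUC: mg ÷ (mg·h/L) = L/h, a clearance.
- AUC/Dose, as printed: (mg·h/L) ÷ mg = h/L, not a clearance.
- (AUC/Dose) × (Dose/AUC) = 1, so the printed formula is the exact reciprocal.

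**Group contrast.** Assume AUC0-24 of 1000 ng·h/mL (1 mg·h/L) in the normal group and 2000 ng·h/mL (2 mg·h/L) in the severe group.

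| | Normal | Severe | Severe/Normal |
|---|---|---|---|
| Dose/AUC0-24 | 50/1 = 50 L/h | 50/2 = 25 L/h | 0.5 |
| AUC0-24/Dose, as printed | 1/50 = 0.02 h/L | 2/50 = 0.04 h/L | 2.0 |

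The ratios do not depend on the assumed AUC level, because the dose cancels. For AUC ratios of 1.0, 1.5, 2.0 and 3.0, the CL/F ratio is 1.00, 0.667, 0.50 and 0.333 with Dose/AUC, and 1.0, 1.5, 2.0 and 3.0 as printed.

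**Check against Table 4.** From the urine definitions,

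CLr = Ae24/AUC = (Ae24/Dose) × (Dose/AUC).

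So CLr equals the fraction excreted times CL/F only if CL/F = Dose/AUC. At the 8% bound with AUC of 1 mg·h/L, Ae24 = 0.08 × 50 = 4 mg and CLr = 4/1 = 4 L/h. With Dose/AUC, 0.08 × 50 L/h = 4 L/h, which agrees. With the printed formula, 0.08 × 0.02 h/L = 0.0016 h/L, which does not.

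**Regression, if Part 2 runs and CL/F is chosen.** On the log scale, ln(AUC/Dose) = −ln(Dose/AUC), so the slope on renal function keeps its size and changes sign, and R² is unchanged. The log scale is an inference: SAP Table 3 lists CL/F as ln, and the regression code in SAP Appendix 1 uses the same prefixed variable name as the mixed-model code for log-transformed data. The regression text itself states no scale.

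On the raw scale the reversal is not an identity, so it was simulated: 5000 runs, lognormal AUC, assumed AUC ratios to normal of 1.2 (mild), 1.5 (moderate) and 2.0 (severe), and eGFR assumed uniform within 10–29.9, 30–59.9, 60–89 and 90–120. The share of runs in which the two raw-scale slopes had opposite signs was:

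| Between-participant CV (assumed) | 8 per group | 6 per group |
|---|---|---|
| 30% | 100% | 100% |
| 50% | 99.7% | 99.2% |
| 70% | 97.1% | 95.8% |

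**Can finished tables be inverted afterwards?** Geometric means and medians reverse their order across groups, and the geometric CV is unchanged. Arithmetic means do not invert: in one simulated group of 8, the arithmetic mean of Dose/AUC was 25.4 L/h, while the reciprocal of the arithmetic mean of AUC/Dose was 23.5 L/h. SAP Table 4 asks for arithmetic means and standard deviations, so those would have to be derived again.

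**The case against.** The strongest reply is that this is a typographical slip that nobody would act on. The cell contradicts its own label, CLr is oriented correctly just below it, the SAP points to standard methods, and a clearance reported in h/L would be noticed. This makes literal use unlikely. It does not remove the error, because Table 3 is the stated derivation and contains the only CL/F formula in either document. An analyst who does the right thing departs from the protocol without any text to support it.

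A second reply is that nothing decisive depends on CL/F. This is correct. SAP Table 3 marks only AUC0-24 and Cmax for model-based analysis, and the decision to start Part 2 uses the AUC0-24 ratio. With a fixed dose, CL/F adds no exposure information beyond AUC0-24, and a correct AUC0-24 would appear in the same summaries.

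Third, the regression consequence needs several conditions together: an AUC0-24 ratio of at least 2.0 for a drug with low urinary recovery, Part 2 carried out, CL/F chosen over CLr, and literal use of the cell. That also stands, so the main consequence is for the group summaries. The check against the urine formulas is likewise only supporting evidence: the documents do not state that relation, and urine is assayed only if the study team decides to. The units argument is enough without it.

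**Conclusion.** The formula is wrong as written: Table 3 defines the reciprocal of the quantity that it names. This follows from units alone and needs no assumed value. If applied literally, a doubling of AUC0-24 would appear as a doubling of apparent clearance instead of a halving, a fourfold discrepancy in the group ratio (2.0 ÷ 0.5). A log-scale regression slope on renal function would be exactly negated, and a raw-scale slope would very probably reverse under the assumptions shown.

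The consequence is confined to an exploratory endpoint and depends on the cell being followed. The primary comparisons and the Part 2 decision are unaffected. The cell should be corrected, but it does not threaten the trial's main conclusions.

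**What to change.** Change the CL/F method in protocol Table 3 to Dose/AUC0-24, and state the same formula in the SAP beside its Table 3. The cost is one table cell and one line, with no additional samples or visits. If the protocol is not otherwise being amended, the SAP line alone can carry the correction: protocol section 9 says "The SAP may modify what is outlined in the protocol where appropriate" and ties an amendment only to major changes in the primary endpoints or their analyses.

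A separate tidy-up, which does not bear on the weight of this point: Vz/F is named for the Part 2 regression but is derived in neither protocol Table 3 nor SAP Table 3. Either delete it from the regression text or add its derivation, with the terminal-phase parameters that it needs, to both tables.
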